7.8.2. Progression-Free Survival

PFS time is defined for all patients and is measured from the date of first dose (Day 1) until (a) treatment failure, (b) relapse after combined remission, or (c) death from any cause, whichever occurs first.

Treatment failure is defined as failing to achieve a combined remission following induction therapy. The date of treatment failure is defined by the earliest bone marrow collection following the first induction attempt regardless of whether the patient received a second induction attempt (unless the second induction resulted in a combined remission in which case "treatment failure" does not apply).

Additional rules for defining PFS time are:

- A patient found to have relapsed after missing one or more scheduled response assessments will have his PFS time end on the scheduled date for the first missed response assessment following the last confirmation of combined remission
- A patient who misses the first scheduled response assessment and who never achieves combined remission will have his PFS time end on the scheduled date for the first response assessment (unless the patient died before this date)

Patients enrolled subsequent to protocol amendment 6 were scheduled to be followed for 2 years following the end-of-study visit, whereas patients enrolled prior to protocol amendment 6 were followed for only 30 days following the end-of-study visit unless they reconsented to the amendment-6, 2-year follow-up period. The definition of PFS time and the following rules for censoring PFS time apply to all patients regardless of follow-up duration.

Rules for censoring PFS time are:

- A patient with PFS continuing as of the date he is lost to follow-up will have his PFS time censored on the date of his last response assessment
- A patient with PFS continuing as of the database lock will have his PFS time censored on the date of his last response assessment

Summary statistics will include the number and percentage of censored PFS times, quartile PFS times, 95% CIs for the quartile PFS times, and KM "survival" percentages¹⁰ with 95% CIs at select milestone times (e.g., 6, 12 and 18 months).

7.8.3. Overall Survival

OS time is defined for all patients and is measured from the date of first dose (Day 1) until death from any cause. Patients enrolled subsequent to protocol amendment 6 were scheduled to be followed for 2 years following the end-of-study visit, whereas patients enrolled prior to protocol amendment 6 were followed for only 30 days following the end-of-study visit unless they reconsented to the amendment-6, 2-year follow-up period. The definition of OS time and the following rules for censoring OS time apply to all patients regardless of follow-up duration.

Rules for censoring OS time are:

- A patient with OS continuing as of the date he is lost to follow-up will have his OS time censored on the date of his last assessment of any type
- A patient with OS continuing as of the database lock will have his OS time censored on the date of his last assessment of any type

Summary statistics will include the number and percentage of censored OS times, quartile OS times, 95% CIs for the quartile OS times, and KM survival percentages with 95% CIs at select milestone times (e.g., 6, 12 and 18 months).

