5.6 Follow-up Assessments

5.6.1 Safety Follow-up (30 Days Post Last Dose)

Patients must have a safety evaluation 30 days after the last dose of study drug. The following assessments will be performed:

- Assess for AEs
 - Ongoing AEs must be followed clinically until the event is resolved, deemed stable, or the patient starts another treatment for their disease
- Record only those medications (prescription, nonprescription, and nutritional supplements) administered in conjunction with an AE, as well

as any antineoplastic therapies initiated since discontinuation of study drug.

5.6.2 Long-term Follow-up (Starting 30 Days Post End of Study out to 2 Years)

Additionally, all study patients will be attempted to be contacted by phone, if possible, every 6 months to assess for date of death, date of stem cell transplant, date of relapse, or continued remission beginning the month after the patient completes the End of Study assessments to 24 months after Day of First Dose regardless of how many cycles a patient receives. When telephone contact is not possible, medical records will serve as the surrogate to assess for these outcomes.

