8.7 Patient Deaths

Every effort will be made in the case of patients who die to determine the cause of death. Information regarding a patient who dies more than 30 days after receiving study drug may be recorded on a Death Report Form (no SAE report is required). An SAE report is recorded only if the event leading up to the patient's death began within 30 days of the last administration of study drug.

The Death Report Form is distinct and separate from the adverse event form included in the case report form.

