- Combined Remission Duration (defined only for patients who achieve a combined remission during the study): time from the earliest date of combined remission (Day 1) until relapse after combined remission
- Stem Cell Transplant Rate: percentage of patients proceeding directly to stem cell transplantation within 90 days after their last dose of study drug

Safety Endpoints (not listed in order of importance)

- 30- and 60-Day Mortality
- Adverse Event Incidence Rates
- Time to neutrophil recovery ≥1x10⁹/L
- Time to platelet recovery ≥100x10⁹/L
- Presence and Severity of Tumor Lysis Syndrome
- Clinical Laboratory Parameters
- Vital Signs

Other Endpoints

Concomitant Medication Usage Rates

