Appendix 2. Sample Table Template

Tolero Pharmaceuticals ALV-101

Patient Disposition (Intent-to-Treat Population) Table X.X

Page 1 of 327

	Alvocidib $20/30 \text{ mg/m}^2$ $(N=3)$	Alvocidib $30/40 \text{ mg/m}^2$ (N=3)	Alvocidib $30/50 \text{ mg/m}^2$ $(N=3)$	Alvocidib $30/60 \text{ mg/m}^2$ $(N=13)$	Study Total (N=22)
Study Center Columbia University Medical Center University of North Carolina Johns Hopkins University	3 (100%)	1 (33.3%) 2 (66.7%) 0	3 (100%) 0	2 (15.4%) 7 (53.8%) 4 (30.8%)	6 (27.3%) 12 (54.5%) 4 (18.2%)
Country United States	3 (100%)	3 (100%)	3 (100%)	13 (100%)	22 (100%)
Protocol Version Amendment 2 Amendment 3 Amendment 4	1 (33.3%) 2 (66.7%) 0	3 (100%) 0	3 (100%) 0	0 0 13 (100%)	1 (4.5%) 8 (36.4%) 13 (59.1%)
Safety Analysis Population Yes	3 (100%)	3 (100%)	3 (100%)	13 (100%)	22 (100%)
Response Evaluated Analysis Population Yes	3 (100%)	3 (100%)	3 (100%)	13 (100%)	22 (100%)
Alvocidib and 7+3 Induction Yes	3 (100%)	3 (100%)	3 (100%)	13 (100%)	22 (100%)

[[]a] Number of weeks from the first dose of alvocidib to withdrawal from study

Source: Data Extract ddmmmyy; SAS (v9.4) ddmmmyy at hh:mm

Statistical Analysis Plan Protocol TPI-ALV-201

Tolero Pharmaceuticals ALV-101	ticals ALV-101	Table X.X Patient Disposition (Intent-to-Treat Population)	X.X sposition t Population)				Page 2 of 327
		Alvocidib 20/30 mg/m² (N=3)	Alvocidib 30/40 mg/m² (N=3)	Alvocidib 30/50 mg/m² (N=3)	Alvocidib 30/60 mg/m² (N=13)	Study Total (N=22)	
	Alvocidib and 5+2 Reinduction Yes No	3 (100%)	1 (33.3%) 2 (66.7%)	3 (100%)	1 (7.7%) 12 (92.3%)	2 (9.1%) 20 (90.9%)	
	HiDAC Consolidation Cycles 0 1 2 3 4	1 (33.3%) 1 (33.3%) 0 1 (33.3%)	2 (66.7%) 0 0 0 0 1 (33.3%)	1 (33.3%) 0 1 (33.3%) 1 (33.3%) 0 1 (33.3%)	9 (69.2%) 3 (23.1%) 1 (7.7%) 0	13 (59.1%) 4 (18.2%) 2 (9.1%) 2 (9.1%) 1 (4.5%)	
	Weeks on Study ^[a] Mean (S.D.) Median Min, Max	19.7 (13.8) 17.7 7.0, 34.4	15.0 (11.0) 9.4 7.9, 27.6	15.0 (8.1) 14.4 7.3, 23.4	8.1 (3.6) 9.0 3.9, 12.3	13.6 (9.1) 10.0 3.9, 34.4	
	Primary Reason Patient was Withdrawn from the Study Completed the Study Death Relapsed Disease (following remission) Lack of Efficacy (failure to achieve remission) Unknown Missing	2 (66.7%) 0 0 0 0 1 (33.3%)	2 (66.7%) 0 0 1 (33.3%) 0	1 (33.3%) 0 1 (33.3%) 1 (33.3%) 0 0	2 (15.4%) 1 (7.7%) 1 (7.7%) 1 (7.7%) 0 8 (61.5%)	7 (31.8%) 1 (4.5%) 2 (9.1%) 3 (13.6%) 1 (4.5%) 8 (36.4%)	

[a] Number of weeks from the first dose of alvocidib to withdrawal from study

Source: Data Extract ddmmmyy; SAS (v9.4) ddmmmyy at hh:mm

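### SAP 7.8.3: overall survival at 12 and 18 months is at risk of upward immortal-time bias from pre-Amendment-6 patients who reconsent after their original follow-up window has closed

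*SAP*

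**What the plan says.** SAP 7.8.3 defines OS for all patients as "measured from the date of first dose (Day 1) until death from any cause". It describes two follow-up regimes. Patients enrolled after Amendment 6 are followed for 2 years after the end-of-study visit. Those enrolled before it "were followed for only 30 days following the end-of-study visit unless they reconsented to the amendment-6, 2-year follow-up period". The OS definition and censoring rules then "apply to all patients regardless of follow-up duration", and a patient still alive "will have his OS time censored on the date of his last assessment of any type". Kaplan-Meier percentages are planned at milestones such as 6, 12 and 18 months. The section has no delayed-entry rule, no truncation at the original window and no sensitivity analysis for the two regimes.

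Three other places bear on this:

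- Protocol 5.6.2 plans contact every 6 months "to 24 months after Day of First Dose regardless of how many cycles a patient receives", with medical records as the fallback. It addresses all study patients, but the SAP makes this follow-up conditional on reconsent for those enrolled before Amendment 6.
- Protocol 8.7: "Information regarding a patient who dies more than 30 days after receiving study drug may be recorded on a Death Report Form". That is optional, and not tied to reconsent.
- The SAP Appendix 2 sample table has the row "Protocol Version Amendment 2 Amendment 3 Amendment 4" with 1, 8 and 13 patients: 22 in all, none enrolled under Amendment 6.

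**The concern.** Between the close of the original window and reconsent, a pre-Amendment-6 patient is not under follow-up. Only survivors of that gap can sign. If a reconsenter is then counted at risk without a break from Day 1, the gap adds person-time in which, by construction, he could not die. Patients who did die in it drop out of the risk set at their last earlier assessment, unless the death is otherwise recorded. The estimated hazard in the gap is too low, and every later point on the curve is raised.

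The late milestones are where this bites. In the sample table the longest time on study plus 30 days is 8.9 months, so on that extract any 12- or 18-month information from these patients would have to come from extended follow-up. Protocol 1.2 motivates the trial by short survival and rapid relapse, so the late OS figures will probably be read when later studies are planned.

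**Working it through.** The documents state no OS target or event count, so there is no figure of the plan's own to reproduce. The check asks what the SAP rule returns when the truth is known.

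**Inputs from the documents**
- Pre-Amendment-6 patients (sample table): 1 + 8 + 13 = 22.
- End of original window, F: mean 13.6 weeks on study plus 30 days, in the SAP's months: (13.6 × 7 + 30)/30.4375 = 4.1 months. Longest: (34.4 × 7 + 30)/30.4375 = 8.9 months.
- Sample-table disposition: 14 of 22 have an entry and one of these is a death, so 13 were off study and not recorded as dead. Gaps are therefore likely.

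**Assumptions**
- Exponential OS with median 12 to 24 months, guided by the median of under 1 to 2 years in Protocol 1.2.
- 13 post-amendment patients. The cohorts listed in Protocol 11.2 add to 3 + 3 + 6 + 3 + 20 = 35, and 35 − 22 = 13.
- Gap from F to reconsent R of 0 to 12 months; 25%, 50% or 100% of those alive at R reconsent (fraction r); no deaths captured without reconsent.

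**Formula.** Let p = 22/35 = 0.629 and 1 − p = 0.371. In the gap the risk set is (1 − p)S(t) from post-amendment patients plus a constant p·r·S(R) of guaranteed survivors, and deaths come only from the first part. In large samples the SAP's curve is:
- in the gap: S(F) × [(1 − p)S(t) + p·r·S(R)] / [(1 − p)S(F) + p·r·S(R)]
- after R: S(t) × [(1 − p) + p·r] / [(1 − p) + p·r·S(R)/S(F)]

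With no gap, S(R) = S(F), the factor is 1 and there is no bias.

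**12-month OS, common F = 4.1**
- Gap 3, median 12, r = 1: S(R)/S(F) = 2^(−3/12) = 0.841. Factor 1/(0.371 + 0.629 × 0.841) = 1.111. True 50.0%, SAP rule 55.6%.
- Gap 3, median 24, r = 0.25: S(R)/S(F) = 2^(−3/24) = 0.917. Factor (0.371 + 0.157)/(0.371 + 0.157 × 0.917) = 1.025. True 70.7%, SAP rule 72.5%.
- Gap 12, median 12, r = 1 (month 12 falls inside the gap): 0.789 × (0.371 × 0.500 + 0.629 × 0.394)/(0.371 × 0.789 + 0.629 × 0.394) = 63.2%, true 50.0%.
- Gap 12, median 24, r = 0.25: 0.888 × (0.371 × 0.707 + 0.157 × 0.628)/(0.371 × 0.888 + 0.157 × 0.628) = 74.9%, true 70.7%.

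**Simulation**, letting time on study vary as in the sample table (median 10.0 weeks, range 3.9 to 34.4), gives the bias in percentage points:

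| Gap (months) | OS at 12 months | OS at 18 months |
|---|---|---|
| 0 | 0 | 0 |
| 3 | +1.4 to +5.4 | +1.2 to +3.5 |
| 6 | +3.0 to +10.6 | +2.6 to +7.5 |
| 12 | +4.1 to +13.6 | +5.3 to +15.5 |

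If only 14 of the 22 have a gap and half reconsent, the bias is about +1.5 to +5 points at 12 months and +1 to +6 at 18 months.

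**Direction.** Now let deaths in non-reconsenters be recorded while their survivors stay censored at the window, with 50% reconsent and gaps of 3 to 12 months. If half of those deaths are captured, the bias is −0.7 to +1.6 points at 12 months and −2.0 to +1.3 at 18. If all are captured, it is −2.6 to −3.6 and −3.8 to −5.7.

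**Does delayed entry repair it?** With the 13 post-amendment patients, yes: about 50% and 35% at 12 and 18 months against a true 50.0% and 35.4% (median 12), and 71% and 59% against 70.7% and 59.5% (median 24). With no post-amendment patients and a 12-month gap, no: about 60% and 47% against 50.0% and 35.4%, because almost nobody is under observation in between.

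**The case against.** The strongest reply is that nothing shows the bias will occur. It needs a gap and unrecorded deaths. Reconsent on study or within the window leaves no gap, and 8 of the 22 sample-table patients have no withdrawal reason recorded. The SAP censors only patients whose survival is continuing, so a gap death that reaches the database counts as an event; Protocol 5.6.2 and 8.7 both offer routes. This stands against any statement that OS is overstated. It does not remove the risk. One route is optional, the other depends on reconsent under the SAP, and recording deaths without the matching survivors creates a bias of its own.

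OS is also a descriptive secondary endpoint in a Phase 1 dose-finding trial. With 22 patients, the 95% interval around 63% is about ±20 points even without censoring: 1.96 × √(0.63 × 0.37/22) = 0.20. That limits the importance, but a wide interval does not correct a shifted estimate.

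Four stronger readings are tempting and not supported:

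- That the Day 1 origin is at fault. The window runs to 30 days after the end-of-study visit, so time up to then is observed for everyone. Only the gap is immortal.
- That the inflation is S(F)/S(R) whatever the reconsent rate. This needs every patient to be pre-amendment with a gap and no late death recorded. The SAP describes post-Amendment-6 enrolment, and the sample table is a format blueprint with a placeholder extract date.
- That PFS, RFS and CR duration carry the same bias. Relapse does not prevent reconsent, event-free patients are censored at the last response assessment, and relapse after missed assessments is backdated. A delayed-entry rule cannot simply be carried over.
- That the transplant rate, "percentage of patients proceeding directly to stem cell transplantation within 90 days after their last dose of study drug", is undercounted because follow-up may end sooner. The sample table records post-study transplants in 3 of 22 patients, all enrolled before Amendment 6, so some were being collected.

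**Conclusion.** The concern holds as a risk, for OS only, and is worth correcting. SAP 7.8.3 as written counts late reconsenters at risk through time they had to survive, and nothing in either document guarantees that deaths in that time are recorded for the others. The likely direction is upward, but neither sign nor size is fixed. Both depend on reconsent dates, the reconsent rate and how late deaths were captured, none of which is given. On the assumptions above, the excess at 12 months is about 1 to 5 points for a 3-month gap and 4 to 14 points for a 12-month gap; with no gap it is zero. These figures are illustrations, not estimates for this trial.

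A related inconsistency holds without assumptions. Extended follow-up ends 24 months after first dose in Protocol 5.6.2 but 2 years after the end-of-study visit in SAP 7.8.3. At the sample table's mean and longest times on study these differ by 13.6 × 7/30.4375 = 3.1 and 34.4 × 7/30.4375 = 7.9 months.

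**What to change.** In SAP 7.8.3:

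1. Count a pre-Amendment-6 patient at risk from Day 1 to the end of the original window and, if reconsent came later, again only from the reconsent date (start/stop intervals). Reconsent on study or inside the window leaves one unbroken interval.
2. State one rule for deaths outside these intervals and apply it alike with and without reconsent. Tabulate reconsent date and last known vital status for every pre-Amendment-6 patient.
3. Add a sensitivity analysis that ends every pre-Amendment-6 patient at 30 days after the end-of-study visit.
4. Show numbers at risk, and do not report milestones beyond a time when almost nobody is under observation. Delayed entry cannot recover the curve there.
5. Give the same end of extended follow-up in the SAP and Protocol 5.6.2.

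The cost is SAP wording plus retrieval of reconsent dates and vital status. Fewer patients will be at risk, intervals will widen, and late OS figures may be lower or go unreported. Where no patient has a gap, the main OS estimate changes only if deaths outside observed time had been counted.

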7.8.4. Relapse-Free Survival Following CR

RFS time is defined only for patients who achieve a CR during the study and is measured from the date of CR (Day 1) until (a) relapse after CR, or (b) death from any cause, whichever occurs first.

An additional rule for defining RFS time is:

 A patient found to have relapsed after missing one or more scheduled response assessments will have his RFS time end on the scheduled date for the first missed response assessment following the last confirmation of CR

Patients enrolled subsequent to protocol amendment 6 were scheduled to be followed for 2 years following the end-of-study visit, whereas patients enrolled prior to protocol amendment 6 were followed for only 30 days following the end-of-study visit unless they reconsented to the amendment-6, 2-year follow-up period. The definition of RFS time and the following rules for censoring RFS time apply to all patients regardless of follow-up duration.

Rules for censoring RFS time are:

- A patient with RFS continuing as of the date he is lost to follow-up will have his RFS time censored on the date of his last response assessment
- A patient with RFS continuing as of the database lock will have his RFS time censored on the date of his last response assessment

Summary statistics will include the number and percentage of patients who achieve a CR, the number and percentage of censored RFS times, quartile RFS times, 95% CIs for the quartile RFS times, and KM "survival" percentages with 95% CIs at select milestone times (e.g., 6, 12 and 18 months).

Two endpoints analogous to relapse-free survival following CR will be analyzed using similar methods.

- Relapse-Free Survival Following Combined CR (defined only for patients who achieve a combined CR during the study): time from the earliest date of combined CR (Day 1) until (a) relapse after combined CR, or (b) death from any cause, whichever occurs first
- Relapse-Free Survival Following Combined Remission (defined only for patients who achieve combined remission during the study): time from the earliest date of combined remission (Day 1) until (a) relapse after combined remission, or (b) death from any cause, whichever occurs first

Response categories included in "combined CR" and "combined remission" are delineated in Section 3.

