7.8.5. Complete Remission Duration

CR duration is defined only for patients who achieve a CR during the study and is measured from the date of CR (Day 1) until relapse.

An additional rule for defining CR duration is:

 A patient found to have relapsed after missing one or more scheduled response assessments will have his CR duration end on the scheduled date for the first missed response assessment following the last confirmation of CR

Patients enrolled subsequent to protocol amendment 6 were scheduled to be followed for 2 years following the end-of-study visit, whereas patients enrolled prior to protocol amendment 6 were followed for only 30 days following the end-of-study visit unless they reconsented to the amendment-6, 2-year follow-up period. The definition of CR duration and the following rules for censoring CR duration apply to all patients regardless of follow-up duration.

Rules for censoring CR duration are:

- A patient who dies while in remission will have his CR duration censored on the date of death
- A patient in remission on the date he is lost to follow-up will have his CR duration censored on the date of his last response assessment
- A patient in remission on the database lock will have his CR duration censored on the date of his last response assessment

Summary statistics will include the number and percentage of patients who achieve a CR, the number and percentage of censored CR durations, quartile CR durations, 95% CIs for the quartile CR durations, and KM "survival" percentages with 95% CIs at select milestone times (e.g., 6, 12 and 18 months).

Two endpoints analogous to CR duration will be analyzed using similar methods.

- Combined CR Duration (defined only for patients who achieve a combined CR during the study): time from the earliest date of combined CR (Day 1) until relapse after combined CR
- Combined Remission Duration (defined only for patients who achieve combined remission during the study): time from the earliest date of combined remission (Day 1) until relapse after combined remission

Response categories included in "combined CR" and "combined remission" are delineated in Section 3.

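### Read literally, the SAP stops the RFS, PFS and CR-duration clock at the last marrow for patients still in remission but counts relapses and deaths learned later, so censoring depends on outcome

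*SAP*

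**What the plan says.** **Censoring.** SAP 7.8.4 (RFS): "A patient with RFS continuing as of the database lock will have his RFS time censored on the date of his last response assessment". SAP 7.8.2 (PFS): "A patient with PFS continuing as of the database lock will have his PFS time censored on the date of his last response assessment". SAP 7.8.5 (CR duration): "A patient in remission on the database lock will have his CR duration censored on the date of his last response assessment". Loss to follow-up is handled the same way. OS is worded differently in SAP 7.8.3: a surviving patient "will have his OS time censored on the date of his last assessment of any type".

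**Events.** RFS and PFS count relapse or death whenever it occurs. CR duration counts relapse, and "A patient who dies while in remission will have his CR duration censored on the date of death". SAP section 7 says that, as a general rule, relapse and death dates are read from the clinical database. None of the three subsections limits events to those found by the last response assessment. A separate rule back-dates some relapses: "A patient found to have relapsed after missing one or more scheduled response assessments will have his RFS time end on the scheduled date" of the first assessment missed.

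**What is collected, and when.** The SAP's definitions section does not define response assessment; its synopsis describes the investigator's review of marrow and blood results. Marrows are scheduled after consolidation cycles 2 and 4 (Protocol 5.4.5) and at End of Study if none was done in the previous 30 days (Protocol 5.5). After that, Protocol 5.6.2 asks for death, transplant, relapse or continued remission every six months by phone, with medical records as the substitute.

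**Who is followed.** The SAP gives patients enrolled after Amendment 6 a two-year follow-up. Earlier patients have 30 days after End of Study unless they reconsented.

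**The concern.** Kaplan-Meier estimation needs a censoring time that does not depend on the patient's outcome. Take two patients whose last marrow is at month 4 after CR, both reached by phone at month 12. One relapsed at month 10 and enters as an event at month 10, at risk for all ten months. The other is in continued remission and is censored at month 4, so eight documented event-free months are discarded. After the last marrow, the risk set keeps mainly patients already known to fail.

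CR duration has a further oddity: a patient who dies in remission stays at risk until death, while one who stays alive in remission leaves at the last marrow.

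The rule reaches PFS, three RFS endpoints and three remission-duration endpoints, which is 7 of the 12 secondary efficacy endpoints in SAP Table 1. The SAP names 6, 12 and 18 months as example milestones, and the last two lie mostly beyond the scheduled marrows.

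**Working it through.** The documents give no RFS, PFS or remission-duration figure, so there is none to reproduce and every size below rests on assumptions.

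**Assumed inputs.** RFS is exponential with median 18 months, so S(t) = 2^(−t/18). The last marrow is uniform 1–6 or 2–8 months after CR. Everyone has 30 days of follow-up. Long-term follow-up ends 22.5 months after CR: the protocol's 24 months from first dose, less an assumed 1.5 months to CR.

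True values: S(6) = 0.7937, S(12) = 0.6300, S(18) = 0.5000, S(22.5) = 0.4204.

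**Closed form, everyone followed, last marrow 1–6 months.** After month 6 every patient who stays event-free to 22.5 months has already been censored. The fraction at risk at t is therefore S(t) − S(22.5), and

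KM(t) / KM(6) = [S(t) − S(22.5)] / [S(6) − S(22.5)].

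- 12 months: (0.6300 − 0.4204) / (0.7937 − 0.4204) = 0.2096 / 0.3733 = 0.561.
- 18 months: (0.5000 − 0.4204) / 0.3733 = 0.0796 / 0.3733 = 0.213.
- Between months 1 and 6 the hazard is λS(t) / [S(t) − S(22.5) + S(22.5)(6 − t)/5], with λ = ln 2 / 18. Integrating gives KM(6) = 0.736.
- KM(12) = 0.736 × 0.561 = 0.41 against a true 0.63. KM(18) = 0.736 × 0.213 = 0.16 against 0.50.

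With the last marrow at 2–8 months the same calculation gives 0.44 and 0.17.

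**Other follow-up patterns.** RFS from simulated Kaplan-Meier curves (200,000–400,000 responders per setting). For reconsent among survivors, 75% of events are relapses and the median from relapse to death is 8 months.

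| Who has long-term follow-up | SAP rule, 12 mo (true 0.63) | SAP rule, 18 mo (true 0.50) | Censored at last documented remission, 12 mo |
|---|---|---|---|
| Unrelated to outcome, 10–100% followed | 0.36–0.44 | 0.14–0.17 | 0.63 |
| Reconsent if alive, 3–18 or 9–15 months after CR, 25–100% of eligible | 0.45–0.52 | 0.18–0.20 | 0.66–0.71 |
| Reconsent if event-free, same windows and shares | 0.51–0.71 | 0.22–0.29 | 0.69–0.81 |
| Nobody | not estimable | not estimable | not estimable |

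If event-free patients reconsent as late as 15–20 months after CR, the 18-month value can also be too high (0.52–0.58).

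The last column shows that changing the censoring date is enough only in the first row. Under reconsent, patients who had an event early never enter long-term follow-up, so the curve is too high. Starting post-End-of-Study time at risk at the reconsent date brings the 12-month value to 0.63–0.64 (window 3–18) or 0.63–0.69 (window 9–15, where nobody may be at risk just before reconsent).

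**Other medians**, follow-up unrelated to outcome, 25–100% followed, 12 months: median 12, true 0.50, SAP rule 0.32–0.36; median 24, true 0.71, SAP rule 0.44–0.49.

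**Numbers at risk.** With 15 responders, all followed, last marrow 1–6 months, about 15 × 0.2096 = 3.1 are at risk at 12 months under the SAP rule, against 15 × 0.63 = 9.4 with documented remission. With 10% followed at random, the risk set at 12 months is empty in 72% of simulated trials under the SAP rule.

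**The case against.** **The term is undefined.** The synopsis does not restrict response assessment to scheduled marrows, and the records allowed by Protocol 5.6.2 may contain local marrow or blood results. The SAP also describes the two-year follow-up and then applies its censoring rules whatever the follow-up length, so its authors had that period in view. This stands: the defect belongs to the literal reading, and one sentence could remove it. Against the wider reading, the SAP never states it and chose broader words for OS.

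**That later relapses count is inferred.** It rests on unrestricted event definitions and a general statement about database dates; relapse criteria are left to the protocol's Appendix E. True, but nothing excludes these events, and relapse dates are collected for this period.

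**The endpoints carry little weight.** Protocol 7.2 calls a formal efficacy analysis inappropriate, the milestones are examples, and few patients will be at risk. This limits the consequence but does not justify discarding time at risk from patients in remission. The transplant-censored versions in SAP Table 3 do not remove the asymmetry.

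**Stronger readings a reader might infer.** One is that the SAP always understates durability. The documents do not support this, because the direction depends on who is followed. Another is that back-dating makes things worse. That rule needs a missed scheduled assessment and none is scheduled after End of Study, so no size can be attached to it. A third is that all long-term follow-up comes from reconsent, because the SAP Appendix 2 table lists all 22 patients under Amendments 2–4. SAP section 9 presents that table as a format blueprint, so it is only suggestive.

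**Conclusion.** The concern holds on the literal text: for patients followed beyond End of Study, a later contact extends time at risk only if it reports an event (or, for CR duration, a death). It falls away if a 5.6.2 contact is meant as a response assessment.

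Under the assumed 18-month median, the 12-month error runs from about 27 points too low (0.36 against 0.63) to about 8 points too high (0.71 against 0.63). At 18 months the value is 33–36 points too low when follow-up is unrelated to outcome (0.14–0.17 against 0.50). The mechanism does not depend on these assumptions; the sizes do. A reader of the report could not tell the direction without knowing who was followed and from when.

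The consequence is confined to descriptive secondary endpoints with few patients at risk. MTD, safety, CR rate and OS censoring are untouched.

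**What to change.** 1. In SAP 7.8.2, 7.8.4 and 7.8.5, censor event-free patients at the last date remission was documented from any source, including 5.6.2 contacts, or state that such a contact is a response assessment. If a marrow-only version is kept, apply the same cut-off to events.
2. For patients whose long-term follow-up comes from reconsent, start post-End-of-Study time at risk at the reconsent date (delayed entry) in the main analysis, because step 1 alone overstates RFS (about 0.69–0.81 against 0.63 at 12 months when only event-free patients reconsent). Where nobody is at risk just before reconsent, omit the milestone or label it as subject to selection.
3. Report the number at risk at each milestone and how many patients have long-term follow-up by enrolment and by reconsent.
4. Reconcile the follow-up length: Protocol 5.6.2 runs to 24 months after first dose, the SAP to two years after the end-of-study visit.

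Cost: wording in three subsections, one sentence on follow-up length, and delayed entry in the Kaplan-Meier analysis. The protocol already collects the outcomes; reconsent dates should be on file. The drawback is that remission confirmed by phone or records is less precise than marrow. Relapses should keep their own dates: dating them at the contact that found them would give a 12-month RFS of 0.68–0.69 against 0.63.
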